1. VERSION HISTORY

Table 1. Summary of Changes

Version/Date	Associated Protocol Amendment	Rationale	Specific Changes
1 17 Mar 2023	Original 25 Jul 2022	N/A	N/A
2 03 Aug 2023	Original 25 Jul 2022	To update the reactogenicity analysis based on CBER feedback.	
Updated to include both related and unrelated AEs within 7 days of each dose for pooling with the reactogenicity data in Section 3.1.1.
 
Added e-diary completion details for each dose to Section 3.4.1 and Section 6.4.2.
 
Specified safety population details for each dose and added e-diary safety population details for each dose to Section 4.
 
Clarified the handling of missing e-diary data in Section 5.3.1.1.
 
In Section 6.1.1 and Section 6.1.2, added sensitivity analyses of the maximum severity of reactogenicity events and AEs.

3 01 Aug 2025	Original 25 Jul 2022	To update the analysis to include reactogenicity events collected in the AE CRF per FDA comments.	
Updated Section 3.5.1 to include Tier 1 events.
 
Updated Section 3.1.1 and Section 4 to include as reactogenicity data, all prompted local reactions and systemic events reported in the AE CRF for 7 days following study intervention administration (Day 1 through Day 7).
 
Added “AE CRF” to Section 5.3.1.1 to clarify that it may be considered reactogenicity data.
 
Replaced “e-diary” with “reactogenicity” in Section 6.1.1.
 
Modified the sensitivity analysis information in Section 3.1.1.3, Section 6.1.1.3, and Section 6.1.2.

2. INTRODUCTION

This SAP provides the detailed methodology for summary and statistical analyses of the data collected in Study C4601012.

This document may modify the plans outlined in the protocol; however, any major modifications of the primary endpoint definition or its analysis will also be reflected in a protocol amendment.

2.1. Modifications to the Analysis Plan Described in the Protocol

There are no changes in any analyses from the plan specified in the protocol.

2.2. Study Objective, Endpoints, and Estimands

The estimands corresponding to each primary are described in Table 2. There are no secondary or exploratory objectives in this study.

Table 2. Study Objective, Endpoints, and Estimands

Type	Objective	Endpoints	Estimands
Primary safety	
 To describe the safety profile of VLA15 as measured by the percentage of participants reporting local reactions, systemic events, AEs, NDCMCs, and SAEs. 	
 Prompted local reactions (pain at the injection site, redness, and swelling). Prompted systemic events (fever, headache, fatigue, muscle pain, and joint pain). AEs. NDCMCs. SAEs. 	
In participants receiving at least 1 dose of study intervention:
 
 The proportion of participants reporting prompted local reactions within 7 days following each study intervention administration. The proportion of participants reporting prompted systemic events within 7 days following each study intervention administration. The proportion of participants reporting AEs through 1 month following each study intervention administration. The proportion of participants reporting NDCMCs throughout the study. The proportion of participants reporting SAEs throughout the study.

2.2.1. Primary Estimands

2.2.1.1. Primary Safety Estimands

The primary estimands for the primary safety objective will use the treatment policy strategy and estimate the safety rate regardless of whether an intercurrent event occurs.

Reactogenicity estimands have the following 5 attributes:

- **Treatment condition:** VLA15 or placebo.

As this is a multidose vaccine safety study, the 2 groups of VLA15 and placebo assignment will be based on the vaccine actually received. Participants will be assigned to the VLA15 group if at least 1 dose of VLA15 was received; participants will be assigned to the placebo group if all of the doses received were only placebo. For participants who erroneously received a combination of VLA15 and placebo (in the VLA15 group), refer to the endpoints in [Section 3](#) for analysis.

- **Population:** Participants as defined by study inclusion/exclusion criteria.
- **Variables:** Each item included in the e-diary from Days 1 through 7 after each dose or any dose with VLA15 or placebo (refer to [Section 3.1.1.1](#) and [Section 3.1.1.2](#)).
- **Population-level summary:** The rates of reporting for each prompted reactogenicity item in the VLA15 group or the placebo group, separately for each age group and for the combined age groups.
- **Intercurrent events:** The intercurrent events for this safety study will be participants who did not complete the study. However, all participants will be followed for safety monitoring until 6 months after the last dose. Therefore, the treatment policy strategy will be used to handle the intercurrent event; all data collected after the intercurrent event will be included in the analysis for safety purposes.

AE, NDCMC, and SAE estimands are defined in the same way as the reactogenicity estimands, except for the variables of AEs through 1 month following each dose of VLA15 or placebo. The analysis will include the proportion of participants reporting NDCMCs or SAEs, beginning with the first dose of VLA15 or placebo, throughout the study (refer to [Section 3.1.1.1](#) and [Section 3.1.1.2](#)).

2.2.2. Secondary Estimands

No secondary estimands are defined in this study.

2.2.3. Additional Estimands

No additional estimands are defined in this study.

2.3. Study Design

This is a Phase 3, randomized, placebo-controlled, observer-blinded trial to evaluate the safety of a 6-valent OspA-based LD vaccine, VLA15, in healthy children 5 through 17 years of age.

Approximately 3550 healthy participants will be recruited from sites in the US and randomized to receive VLA15 or placebo (saline). Randomization will be stratified by age at the time of study entry (5 through 11 and 12 through 17 years), with a minimum of 600 participants enrolled in each age group. Within each age group, site-based randomization will be used to assign individuals to groups. Randomization will occur after informed consent and eligibility review. Participants will be randomized in a 3:1 ratio to receive VLA15 or placebo. The primary series dosing schedule will be a 3-dose series given at Months 0, 2, and 6. A booster dose will be given approximately 12 months after primary series completion at Month 18.

Vaccine Safety

AEs will be collected through 1 month following each study intervention administration. NDCMCs and SAEs will be collected throughout the study. E-diaries will be used to collect prompted local reaction and systemic event data for 7 days after each vaccination (Days 1 through 7, where Day 1 is the day of vaccination) for all participants. Reported Grade 3 reactogenicity will be assessed by the study site to determine if an unscheduled visit is required.

The approximate duration of the study for each participant is 24 months. Participants who withdraw after randomization will not be replaced.

3. ENDPOINTS AND BASELINE VARIABLES: DEFINITIONS AND CONVENTIONS

3.1. Primary Endpoints

3.1.1. Primary Safety Endpoints

Primary safety endpoints include both reactogenicity data and AEs collected from the e-diary and the AE CRF.

Based on feedback from the FDA on multiple vaccine programs, reactogenicity data will utilize both e-diary data (prompted local reactions and systemic events) and reactogenicity events reported in the AE CRF during the e-diary collection period.

Since the AE CRF does not designate a specific page to collect reactogenicity data for an untransmitted e-diary, Pfizer has adopted a process of providing a listing of AEs reported within 7 days after vaccination for the clinical team to review and determine (“flag”) which PTs should be considered reactogenicity events before the database lock. AEs reported on the same day of vaccination that are missing a start time are defaulted to AEs reported after vaccination. Following these review steps, those AEs reported within 7 days after vaccination that match flagged PTs will be considered reactogenicity data. If the same reactogenicity event is reported on the same day from both the e-diary and the AE CRF, the highest grade from the 2 data sources will be used for that specific day for analysis.

It should be noted that the data collection in the AE CRF is different from that of the e-diary:

- For redness, swelling, and fever, the measured size of redness and swelling at the injection site and temperature are recorded in the e-diary but not in the AE CRF. As the missing e-diary entries are monitored in an ongoing review of the prompted reactions reported in the AE CRF, any measurement recorded in the query response will be considered for the primary analysis, using the data handling memo for analysis purposes. For the 7 days, only the maximum grading from both sources will be used for the aggregated severity analysis.
- For pain at the injection site and all other systemic events, the severity grading algorithm for the e-diary data and the AE CRF may not be the same. Pfizer will choose the highest severity grade.

Any AEs recorded on the AE CRF for 7 days following study intervention administration (Day 1 through Day 7) that are considered local reactions or systemic events will be consolidated with the e-diary data and included in the reactogenicity report.

The subsections below describe how to derive each safety endpoint.

3.1.1.1. Local Reactions

The local reactions reported in the e-diary are redness, swelling, and pain at the injection site from Day 1 through Day 7 after each vaccination dose, where Day 1 is the day of each dose of VLA15 or placebo. Any reactogenicity events reported in the AE CRF during the e-diary collection period are included in the derivation discussed below.

This section describes derivations with details for the assessment of local reactions, ie, presence, maximum severity, duration, and onset day of local reactions.

3.1.1.1.1. Presence of Local Reactions Within 7 Days After Vaccination

For the summary of the presence (yes or no) of a local reaction during the interval from Day 1 through Day 7 after vaccination, where Day 1 is the day of each vaccination dose, the following 6 variables are derived for each participant in the e-diary safety population:

- Presence (yes or no) of each local reaction on any day (Day 1 through Day 7) for each dose of VLA15 or placebo
- Presence (yes or no) of each local reaction on any day (Day 1 through Day 7) for any dose of VLA15 or placebo

The derivation is described in [Table 3](#).

Table 3. Derived Variables for Each Local Reaction

Variable ^a	Yes (1)	No (0)	Missing (.)
Any day (Days 1-7) for each dose	Participant reports the reaction as “yes” on any day (Days 1-7) for each dose of VLA15 or placebo.	Participant reports the reaction as “no” on all 7 days or as a combination of “no” and “missing” on all 7 days for the dose.	Participant reports the reaction as missing on all 7 days for the dose.
Any day (Days 1-7) for any of the 4 doses	Participant reports the reaction as “yes” on any day (Days 1-7) for any dose of VLA15 or placebo.	Participant reports the reaction as “no” on all 7 days or as a combination of “no” and “missing” on all 7 days on any dose of the primary series and booster dose.	Participant reports the reaction as “missing” on all 7 days on any dose of the primary series and booster dose.

a. The variable will be defined for each of the 3 local reactions. For participants who received mixed vaccines across doses (eg, VLA/placebo/VLA, or placebo/VLA15/placebo), only the reactogenicity after VLA15 will be included, and the dose number will be based on the actual dose of VLA15. Reactions reported after placebo was given erroneously will not be counted in the VLA15 group.

- Presence (yes or no) of any local reaction on any day (Day 1 through Day 7) for each dose of VLA15 or placebo
- Presence (yes or no) of any local reaction on any day (Day 1 through Day 7) for any dose of VLA15 or placebo

For any local reaction on any day, a similar definition can be applied as given in Table 4.

Table 4. Derived Variables for Any Local Reaction

Variable	Yes (1)	No (0)	Missing (.)
Any day (Days 1-7) for each dose	Participant reports any local reaction as “yes” on any day (Days 1-7) for the dose.	Participant reports all reactions as “no” on all 7 days or as a combination of “no” and “missing” on all 7 days for all 3 local reactions for the dose.	Participant reports all local reactions as “missing” on all 7 days for the dose.
Any day (Days 1-7) for any of the 4 doses	Participant reports any local reaction as “yes” on any day (Days 1-7) for any dose of the primary series and booster dose.	Participant reports all reactions as “no” on all 7 days or as a combination of “no” and “missing” on all 7 days for all 3 local reactions for any dose of the primary series and booster dose.	Participant reports all local reactions as “missing” on all 7 days for any dose of the primary series and booster dose.

3.1.1.1.2. Maximum Severity of Local Reactions Within 7 Days After Vaccination

The grading of local reactions is listed below in Table 5. Age at each vaccination dose will be used to determine the grading scale for local reactions.

Table 5. Grading Scale for Local Reactions

	Mild Grade 1	Moderate Grade 2	Severe Grade 3	Grade 4 ^a
Participants ≥5 to <12 Years Old				
Redness	0.5 cm to 2.0 cm (1 to 4 caliper units from the e-diary) or mild from the AE CRF	>2.0 cm to 7.0 cm (5 to 14 caliper units from the e-diary) or moderate from the AE CRF	>7 cm (>14 caliper units from the e-diary or severe from the AE CRF	Necrosis or exfoliative dermatitis
Swelling	0.5 cm to 2.0 cm (1 to 4 caliper units from the e-diary) or mild from the AE CRF	>2.0 cm to 7.0 cm (5 to 14 caliper units from the e-diary) or moderate from the AE CRF	>7 cm (>14 caliper units from the e-diary or severe from the AE CRF	Necrosis
Pain (at the injection site)	Does not interfere with activity (mild from the e-diary or the AE CRF)	Interferes with activity (moderate from the e-diary or the AE CRF)	Prevents daily activity (severe from the e-diary or the AE CRF)	Emergency room visit or hospitalization for severe pain at the injection site
Participants ≥12 Years Old				
Redness	>2.0 cm to 5.0 cm (5 to 10 caliper units from the e-diary) or mild from the AE CRF	>5.0 cm to 10.0 cm (11 to 20 caliper units from the e-diary) or moderate from the AE CRF	>10 cm (>20 caliper units from the e-diary) or severe from the AE CRF	Necrosis or exfoliative dermatitis
Swelling	>2.0 cm to 5.0 cm (5 to 10 caliper units from the e-diary) or mild from the AE CRF	>5.0 cm to 10.0 cm (11 to 20 caliper units from the e-diary) or moderate from the AE CRF	>10 cm (>20 caliper units from the e-diary) or severe from the AE CRF	Necrosis
Pain (at the injection site)	Does not interfere with activity (mild from the e-diary or the AE CRF)	Interferes with activity (moderate from the e-diary or the AE CRF)	Prevents daily activity (severe from the e-diary or the AE CRF)	Emergency room visit or hospitalization for severe pain at the injection site

- a. Grade 4 assessment should be made by an investigator; Grade 4 will not be collected in the e-diary but will be collected in the AE CRF.

The following variables are derived for each participant:

- Maximum severity of each local reaction on any day (Day 1 through Day 7) for each dose

The maximum severity (highest grading) of each local reaction within 7 days after each vaccination dose will be derived. It should be noted that for participants in the VLA15 group, if a participant erroneously received placebo, the data after the placebo dose will not be derived. The maximum severity will be derived as follows:

- “Missing,” if values are missing for all days (Day 1 through Day 7)
- 0, if the participant reports all reactions as “no” or a combination of “missing” and “no” for all days (Day 1 through Day 7)
- *Highest grade* (maximum severity) within 7 days after vaccination (either from the e-diary data or from the AE CRF) if the answer is not “no” for at least 1 day

- Maximum severity of each local reaction on any day (Day 1 through Day 7) for any dose

The maximum severity (highest grading) of each local reaction within 7 days after any vaccination dose will be derived after any VLA15 dose for the VLA15 group, and after any placebo dose for the placebo group, and will be based on the variable of the maximum severity of each local reaction for each dose. Reactions reported after placebo was given erroneously will not be counted in the VLA15 group.

- Maximum severity of any local reaction on any day (Day 1 through Day 7) for each dose

The maximum severity for any local reaction on any day for each dose will be derived in the bullet list below. Again, the data after administration of placebo for participants in the VLA15 group will not be used for derivation:

- “Missing,” if values are missing for all days (Day 1 through Day 7) across all 3 local reactions
- 0, if the participant reports all reactions as “no” or a combination of “missing” and “no” for all days (Day 1 through Day 7) for all individual local reactions
- *Highest grade* (maximum severity) within 7 days after vaccination if the answer is not “no” for at least 1 day, for at least 1 local reaction

- Maximum severity of any local reaction on any day (Day 1 through Day 7) for any dose

The maximum severity for any local reaction on any day will be derived after any VLA15 dose for the VLA15 group, and after any placebo dose for the placebo group, based on the variable of the maximum severity for any local reaction for each dose. Reactions reported after placebo was given erroneously will not be counted in the VLA15 group.

3.1.1.1.3. Duration of Each Local Reaction After Each Dose and Any Dose

The duration of each local reaction will be calculated in days as (resolution date of reaction - start date of reaction + 1) after each dose. Resolution of the event is the last day on which the event is recorded in the e-diary (or the AE CRF), or the date the event ends if it is unresolved during the participant's e-diary recording period (the end date collected on the CRF) or AE stop date, whichever is longer, unless chronicity is established. If there is no known end date, the duration will be considered unknown and set to "missing." Participants with no reported reaction have no duration.

As this study includes multiple vaccination doses, the date that the reaction ended for one dose should not be after the date of the subsequent dose. Therefore, if a reaction was ongoing at the time of a subsequent dose, the end date for the reaction after the previous vaccination would be the day before the subsequent dose date, which will be used for the duration computation.

The duration for each local reaction after any dose will be derived after any VLA15 dose for the VLA15 group, and after any placebo dose for the placebo group, based on the total duration across all doses for each local reaction.

For the participants of the VLA15 group who received placebo in error, reactogenicity data after placebo administration will not be included in the derivation.

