6.1.1. Administration

Participants will receive 1 dose of VLA15 or placebo at each vaccination visit (Visits 1, 2, 3, and 6) in accordance with the study's [SoA](#).

VLA15 or placebo should be administered intramuscularly by injecting 0.5 mL into the deltoid muscle, preferably of the nondominant arm.

Standard vaccination practices must be observed and vaccine must not be injected into blood vessels. Appropriate medication and other supportive measures for management of an acute hypersensitivity reaction should be available in accordance with local guidelines for standard immunization practices.

Administration of study interventions should be performed by an appropriately qualified, GCP-trained member of the study staff (eg, physician, nurse, physician's assistant, nurse practitioner, pharmacist, or medical assistant) as allowed by local, state, and institutional guidance.

Study intervention administration details will be recorded on the CRF.

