3.1.1.1.4. Onset Day of Each Local Reaction After Each Dose and Any Dose

The onset day of each local reaction will be derived after each dose. Onset day is defined as the first day of reporting any reaction of any severity.

The onset day for each local reaction after any dose will be derived after any VLA15 dose for the VLA15 group, and after any placebo dose for the placebo group, based on the variable of the first (earliest) onset day for each local reaction across all doses.

For participants in the VLA15 group with placebo administration in error, reactogenicity data after placebo administration will not be included in the derivation.

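### The any-dose duration sums reaction days over up to four doses, so it mixes how often a child reacted with how long reactions lasted

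*SAP*

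**What the plan says.** SAP 3.1.1.1.3 first defines one duration per reaction per dose, "calculated in days as (resolution date of reaction - start date of reaction + 1) after each dose". It then derives the any-dose value "based on the total duration across all doses for each local reaction", using VLA15 doses in the VLA15 group and placebo doses in the placebo group. Four doses are planned (Protocol 6.1.1). SAP 3.1.1.2 handles systemic events in a similar way. SAP 6.1.1.2 lists duration in days, after each dose and after any dose, as a supplementary analysis.

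The neighbouring any-dose variables are not sums. Onset is "based on the variable of the first (earliest) onset day for each local reaction across all doses" (SAP 3.1.1.1.4). Severity is the highest grade and "will be based on the variable of the maximum severity of each local reaction for each dose" (SAP 3.1.1.1.2).

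Two further rules in SAP 3.1.1.1.3 concern the end date:

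- "If there is no known end date, the duration will be considered unknown" and is set to missing.
- If a reaction is still ongoing at the next vaccination, "the end date for the reaction after the previous vaccination would be the day before the subsequent dose date".

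The SAP does not say how a total is formed when one of its components is missing.

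**The concern.** A reader who sees a duration in days expects the length of a reaction. The any-dose onset and severity each describe a single episode: the earliest and the worst. The any-dose duration describes none. It grows with the number of doses a child received and reacted to, and nothing in the SAP labels it as cumulative.

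What is at stake is how the table is read across arms. If children on VLA15 react to more doses than children on placebo, the any-dose row will show longer durations on vaccine even when no single reaction lasts longer. In a study whose only objective is to describe safety, that is an avoidable misreading.

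The end-date rules raise a smaller question. A reaction known to be ongoing at the next dose keeps a duration. A reaction last known to be ongoing at some other contact, with no stop date obtained, loses its duration although a minimum is known. This can happen after the booster, or when no further dose is given, because no later dose then supplies an end date.

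**Working it through.** The documents give no duration figure, so there is none to reproduce. The check applies the SAP's rules to assumed inputs.

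**Inputs.** From the documents: four doses; the per-dose formula and the summing rule (SAP 3.1.1.1.3); the visit windows (Protocol 1.3). Assumed, because the documents give no values: the per-dose reaction rate p, the episode length L, and the share of end dates missing.

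**Step 1: one child.** Four reactions of 2 days give 4 × 2 = 8 days. One reaction of 8 days also gives 8 days. The longest single-dose duration would be 2 and 8 days.

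**Step 2: mean among children who react at least once.** With the same p at each dose, independent doses and fixed L, the expected number of episodes is 4p and the probability of any reaction is 1 − (1 − p)^4. The mean total among reactors is L × 4p / [1 − (1 − p)^4]. With L = 2 days:

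| p | Episodes per reactor | Mean any-dose total (days) |
|---|---|---|
| 0.1 | 1.163 | 2.33 |
| 0.2 | 0.8 / 0.5904 = 1.355 | 2.71 |
| 0.5 | 2.133 | 4.27 |
| 0.7 | 2.8 / 0.9919 = 2.823 | 5.65 |
| 0.9 | 3.600 | 7.20 |

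If placebo had p = 0.2 and VLA15 p = 0.7, the gap would be 5.65 − 2.71 = 2.94 days, although every episode lasts 2 days in both arms.

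The gap depends on independence. If reactions were perfectly correlated within a child, the probability of any reaction would be p. Both arms would then read 2 × 4p / p = 8 days and the gap would vanish, but both figures would be four times the episode length.

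**Step 3: the longest episode as an alternative.** Let 95% of episodes last 2 days and 5% last 10 days, so the per-episode mean is 0.95 × 2 + 0.05 × 10 = 2.40 days in either arm.

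- Sum: 2.40 × 1.355 = 3.25 days at p = 0.2, and 2.40 × 2.823 = 6.8 days at p = 0.7.
- Longest: 2 + 8 × [1 − (1 − 0.05p)^4] / [1 − (1 − p)^4], which is 2.5 days at p = 0.2 and 3.1 days at p = 0.7.

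The longest episode removes most of the distortion but not all of it. A per-episode summary gives 2.40 days in both arms.

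**Step 4: unknown end dates.** In the same mix, suppose a share m of the 10-day episodes lacks an end date. The observed per-episode mean is [1.9 + 0.5(1 − m)] / [0.95 + 0.05(1 − m)]: 2.36, 2.28 and 2.21 days at m = 10%, 30% and 50%, against a true 2.40. If end dates are missing regardless of length, this mean is not biased.

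For the any-dose total at p = 0.7 and m = 30%, a simulation of 400,000 children gives 6.43 days if a missing component makes the whole total missing, and 6.36 days if the remaining components are summed. The true value is about 6.8. The choice between the two matters little, but the SAP does not make it.

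**Step 5: the cap at the next dose.** For a reaction starting on the day of dosing, the longest countable duration is the interval to the next dose: 50 to 70 days after Dose 1, 172 − 70 = 102 to 192 − 50 = 142 after Dose 2, and 535 − 192 = 343 to 555 − 172 = 383 after Dose 3. The cap will rarely bind. No dose follows the booster, so no cap applies there.

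**The case against.** The strongest defence is that total days with a symptom is a legitimate measure of cumulative burden, and that it was prespecified. Per-dose durations are reported beside it, so four 2-day reactions appear as 2 days in each of four per-dose summaries. The SAP specifies no between-arm estimate of duration. The longest-episode alternative also rises with the number of doses reacted to. All of this stands. It shows that the distortion is confined to the any-dose row, and that a per-episode summary is the cleaner alternative. It does not justify calling a sum a duration.

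On missing end dates, a reader might infer that the truly prolonged reactions are excluded. The documents do not support that. A reaction unresolved when the diary ends takes its CRF end date or AE stop date, and one ongoing at the next dose is kept with a capped end. Protocol 8.3.3 requires sites to obtain stop dates for reactions ongoing on the last completed diary day, and the schedule of activities collects them at Visits 2, 3, 4 and 7. An end date may also be unknown because contact was lost, whatever the reaction's length. Only the duration value goes missing; the reaction still counts for presence, severity and onset.

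**Conclusion.** The point holds for the any-dose duration of local reactions and, by reference, of systemic events. As defined, it equals the episode length for a child who reacts once and up to four times that for a child who reacts equally to all four doses. The apparent gap of about 2.9 days between arms with identical 2-day episodes rests on assumed per-dose rates of 0.2 and 0.7 and on independent doses. It illustrates the mechanism and is not a forecast.

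A reader might go further and conclude that neither the typical nor the worst duration is described correctly. That does not follow, because the per-dose summaries are untouched by the sum. The missing-end-date rule is secondary: the reported maximum may be understated if longer reactions more often lack an end date, which is plausible but not shown.

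The analysis is supplementary in a descriptive study without a hypothesis, and no primary proportion changes. The change is desirable rather than essential.

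**What to change.** In SAP 3.1.1.1.3, with the same wording applied through 3.1.1.2:

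1. Summarise any-dose duration over episodes, with one value per reaction per dose. Alternatively, use the longest single-dose duration and note that it still rises modestly with the number of doses reacted to.
2. If the sum is kept, present it separately, labelled as cumulative days with the reaction, and state what happens when one component is missing.
3. For a reaction with no known end date, show its duration as at least x days, counted to the last date it was known to be ongoing. Report the number of such reactions by arm.

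The cost is a few sentences in the SAP and minor programming of one supplementary table. No new data collection is needed.
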